7 STUDY PROCEDURES

Detailed descriptions of subject evaluations required for this protocol are described in this section. These evaluations will be performed during the indicated days and weeks of the study (see the study schedules of events in [Appendix 1](#), No Attack, [Appendix 2](#), Initial Icatibant-treated Attack, and [Appendix 3](#), Subsequent Icatibant-treated Attacks).

All data collected are to be recorded on the appropriate CRF or diary page.

Details for study procedures including sample collection are described in the Laboratory Manual for this study.

7.1 Informed Consent

Prior to conducting any study-related procedures, written informed consent must be obtained from the subject's parent(s) or legal guardian(s) and assent from the subject (if applicable).

The nature, scope, and possible consequences, including risks and benefits, of the study will be explained to the subject, the subject's parent(s), or the subject's legal guardian(s) by the investigator or designee in accordance with the guidelines described in Section [11.4](#). Documentation and filing of informed consent documents should be completed according to Section [11.4](#).

7.2 Study Entrance Criteria

At screening, each subject will be reviewed for eligibility against the study entrance criteria. Subjects who do not meet the study entrance criteria will not be allowed to participate in the study. The reason(s) for the subject's ineligibility for the study will be documented.

7.3 Confirmation of Study Eligibility

Subject eligibility according to the study inclusion and exclusion criteria will be confirmed at the screening and pretreatment (baseline) visits on the basis of review of the study entrance criteria.

7.4 Demographics

Subject demographic information including gender, date of birth, and race will be collected prior to the subject receiving the first dose of investigational product.

7.5 Medical History

Medical history will be recorded in the CRF. Details of prior HAE attacks (eg, typical frequency, symptom duration, onset of relief, and type and frequency of medical interventions required) will be obtained at screening through pretreatment on Day 1. Other important medical events, menstrual cycle history in females (see Section [7.6](#)), and concomitant medication and illnesses will be recorded at other visits on the appropriate CRF pages. Any existing medical condition present prior to the time of the first dose will be reported as medical history.

7.6 Menstrual Cycle History

A menstrual cycle history will be determined historically for female subjects and will be recorded in the CRF. The timing of the blood sampling with respect to the menstrual cycle must be known to inform the interpretation of any potential changes in reproductive hormones in adolescent females, because of the normal cyclical rise and fall of reproductive hormones of the menstrual cycle.

Instructions for investigators:

To assist in this determination, investigators should obtain the following information and document in the CRF.

- Age of menarche
- Normal duration of menstrual flow
- Normal interval in between menstrual periods
- Date of last onset of bleeding
- Prospectively ask female subjects to write down subsequent dates of onset of bleeding and cessation of bleeding between Day 1 and Day 90
- Date of ovulation (sometimes called ovulation pain, mid-cycle pain or mittelschmerz) may also be documented if subjects can identify this feeling

7.7 Height and Weight

Height and weight will be recorded for all subjects.

7.8 Pubertal Status Determination

The investigator will perform an examination for all subjects to determine whether they are prepubertal or pubertal/postpubertal. A description of the sexual maturation scale described by Marshall and Tanner (1969 and 1970) is provided in [Appendix 4](#).

7.9 Investigational Product Administration

Subjects will receive treatment with icatibant as a single, weight-adjusted dose of 0.4 mg/kg administered as an abdominal SC injection up to a maximum dose of 30 mg. Treatment with icatibant should be administered within 12 hours of onset of an acute HAE attack.

Pubertal/postpubertal subjects that present with a subsequent attack at least 3 days after prior treatment (see Section 4.1.3) may receive further treatment with icatibant for a total of 3 icatibant treatments. For subsequent attacks, study drug may be administered by study site personnel at the hospital/study center or by qualified home healthcare personnel at the subject's home. Alternatively, a parent/legal guardian/caregiver will be allowed to administer or the subject (under the supervision of a parent/legal guardian/caregiver) will be allowed to self-administer the investigational product after having received appropriate training. For all subsequent laryngeal attacks, subjects should be advised to seek medical attention in an appropriate healthcare facility immediately following treatment with icatibant.

See the Pharmacy Manual for additional instructions regarding dose calculation and administration.

7.10 Pharmacokinetic Assessments

7.10.1 Pharmacokinetic Variables

Individual patient PK variables for icatibant and major metabolites will be determined from the respective plasma concentration time profiles where appropriate, using noncompartmental methods.

A population PK model will be derived to evaluate the correlation of key covariates (ie, age, body weight, gender) on the PK profile of icatibant.

Pharmacokinetic variables will be determined by full sampling and noncompartmental methods where possible, and elsewhere by sparse sampling (at least 4 to 7 time points) and a population PK approach using nonlinear mixed effects modeling software.

Primary and secondary pharmacokinetic parameter estimates will be reported and include time to peak concentration (T_{max}), actual peak (C_{max}) and minimum (C_{min}) concentrations, total body clearance (CL/F), actual AUC_{0-last} and AUC_{0-inf} , mean residence time (MRT), volume of distribution at steady state (V_{ss}/F) and terminal elimination half-life ($t_{1/2}$).

The methods to be used for estimation of PK parameter values are described in Section 10.5.1.

7.10.2 Pharmacokinetic Sampling

Sampling for PK assessments will be collected according to the schedule of events provided in [Appendix 1](#) (No Attack) and [Appendix 2](#) (Initial Icatibant-treated Attack). Pharmacokinetic assessments are not conducted during subsequent attacks.

The time of investigational product administration on Day 1 will be designated as Time 0. All post-treatment assessments will be calculated from the time of investigational product administration. Detailed sample collection, processing, and shipping instructions will be provided in the study Laboratory Manual.

Blood samples for determination of plasma concentrations of icatibant in pubertal/postpubertal subjects will be collected on Day 1 at pretreatment, and at 15 (± 5) minutes, 30 (± 5) minutes, 45 (± 5) minutes, 1 hour (± 10) minutes, 2 hours (± 10) minutes, 4 (± 0.5) hours, and 6 (± 0.5) after treatment.

Blood samples for determination of plasma concentrations of icatibant in prepubertal subjects will be collected on Day 1 at pretreatment, and at 15 (± 5) minutes, 30 (± 5) minutes, 2 hours (± 10) minutes, 4 (± 0.5) hours, and 6 (± 0.5) hours after treatment.

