1.2 Previous Clinical Studies

1.2.1 Pharmacokinetics of Icatibant

The pharmacokinetic (PK) properties of icatibant have been characterized extensively in studies using both IV and SC administration to healthy adult subjects and adult subjects with HAE. The PK profile of icatibant in adults with HAE (JE049-2101) is similar to that in healthy adults.

After SC administration of a single 30 mg dose of icatibant to healthy adult subjects (N=96), a mean (\pm standard deviation) maximum observed plasma concentration (C_{max}) of 974 ± 280 ng/mL was observed after approximately 0.75 hours. The mean area under the concentration-time curve ($AUC_{0-\infty}$) after a single 30 mg dose was 2165 ± 568 ng•hr/mL, with no evidence of accumulation of icatibant after three 30 mg doses administered 6 hours apart.

Plasma clearance after SC administration of icatibant was 245 ± 58 mL/min with a mean elimination half-life of 1.4 ± 0.4 hours and volume of distribution at steady state (V_{ss}) of 29.0 ± 8.7 L. The information obtained from Phase III clinical studies clearly demonstrated that SC icatibant 30 mg is a clinically safe and effective treatment for attacks of acute angioedema across a wide range of subject demographics, including age, sex, and body weight.

Icatibant is extensively metabolized by proteolytic enzymes to inactive metabolites that are primarily excreted in the urine, with less than 10% of the dose eliminated as unchanged drug. Icatibant is not degraded by oxidative metabolic pathways, and is not an inhibitor of major cytochrome P450 (CYP) isoenzymes (CYP 1A2, 2A6, 2B6, 2C8, 2C9, 2C19, 2D6, 2E1, and 3A4) and is not an inducer of CYP 1A2 and 3A4.

Clinical PK studies demonstrate that for mild to moderate impairment of renal or hepatic function no dose adjustment is necessary. In 10 subjects with hepatorenal syndrome (glomerular filtration rate (GFR) 30 to 60 mL/min), clearance of icatibant was not dependent on renal function. Icatibant clearance in subjects with a wide range of hepatic impairment (Child-Pugh score ≥ 7 and ≤ 15) was similar to that in healthy subjects.

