10.5.1 Estimation of PK Parameters

10.5.1.1 Noncompartmental Modeling

For subjects in whom the number of samples is sufficient to permit noncompartmental modeling, individual and mean PK parameters will be computed for icatibant and metabolites (M1 and M2) using standard noncompartmental methods, where possible, using the WinNonLin software package (Pharsight Corp., Mountain View, CA). For descriptive statistical tabulation of mean plasma concentrations and graphical displays, nominal collection times will be used, while all PK analysis and parameter calculations will use actual collection times. Plasma concentrations <limit of quantification (LOQ) will be treated as 0 for the calculation of the descriptive statistics for plasma concentrations at each sampling time. For the pharmacokinetic analysis, plasma concentrations <LOQ that occurred from predose to the first concentration \geq LOQ will be treated as 0 and those that occur thereafter will be treated as missing.

Pharmacokinetic parameter estimates will include, where appropriate: icatibant and metabolite concentrations at each sampling time, T_{max} , actual peak (C_{max}) and minimum (C_{min}) concentrations, CL/F, AUC_{0-last} and AUC_{0-inf} , MRT, volume of distribution at steady state (V_{ss}/F) and $t_{1/2}$.

The distribution of continuous data will be evaluated using parametric tests. A transformation, such as logs, will be used where appropriate. Multiple regression analysis, with an appropriate transformation on the dependent variable, will be used to assess the contribution of potential PK covariates while controlling for demographic covariates (eg, subject's age and gender) to the inter-subject variability of icatibant PK parameters. The multivariable analysis will be considered the primary statistical analysis. A p-value of 0.05 will be considered statistically significant for all analyses.

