- ^b A subject’s classification as prepubertal or pubertal/postpubertal will be determined at the Day 1 pretreatment visit. Note that a subject classified as pubertal/postpubertal at screening will not require further evaluation of pubertal status during the study.
- ^c These assessments may be conducted by telephone contact.
- ^d The PK sampling times shown are for pubertal/postpubertal subjects. Prepubertal subjects will have blood samples drawn on Day 1 prior to dosing and at 15 (±5) minutes, 30 (±5) minutes, 2 hours (±10 minutes), 4 (±0.5) hours, and 6 (±0.5) hours post dose as indicated in Section 8.3.2.
- ^e A subject may be discharged after completion of all assessments at 6 hours post treatment, if deemed medically stable in the investigator’s clinical judgment and the subject’s HAE symptoms have resolved (the subject’s investigator-rated symptom score = zero, denoting the absence of symptoms). If this is the case, the assessments scheduled for 8 hours post treatment will be omitted with the exception of subject self-assessment of HAE-related pain using the diary FPS-R.
- ^f If the subject’s HAE symptoms have not resolved at 6 hours post treatment (the subject’s investigator-rated symptom score ≠ zero) and the subject is not to be discharged after completion of assessments at the 6-hour time point, the assessments indicated will be performed at both 6 AND 8 hours post treatment.
- ^g If the subject’s HAE symptoms have not resolved at 6 hours post treatment (the subject’s investigator-rated symptom score ≠ zero) and the subject is not to be discharged after completion of assessments at the 6-hour time point, the assessments indicated will be performed at either 6 OR 8 hours post treatment.
- ^h For all subjects who remain enrolled in the study for longer than 6 months, a telephone contact will be scheduled every 6 months to collect information concerning HAE attacks not treated with icatibant in the study.

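### Prepubertal PK sampling has no point between 30 minutes and 2 hours, so noncompartmental Cmax and Tmax comparisons between pubertal groups are confounded with the blood-draw schedule

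*Protocol*

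**What the plan says.** **Sampling.** Protocol Section 7.10.2 gives two schedules. For older subjects, samples for "icatibant in pubertal/postpubertal subjects will be collected on Day 1 at pretreatment, and at 15" minutes, then 30 and 45 minutes and 1, 2, 4 and 6 hours. For the younger group, samples for "icatibant in prepubertal subjects will be collected on Day 1 at pretreatment, and at 15" minutes, then 30 minutes and 2, 4 and 6 hours. Section 8.3.2 repeats both schedules. Appendix 2, footnote d repeats the younger one: "Prepubertal subjects will have blood samples drawn on Day 1 prior to dosing and at 15" minutes, and so on, again with nothing at 45 minutes or 1 hour. The difference is therefore deliberate and not a typing slip.

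**Time to peak.** The only figure is in Section 1.2.1, from healthy adults given 30 mg subcutaneously: a mean Cmax of 974 (SD 280) "ng/mL was observed after approximately 0.75 hours". No pediatric Tmax is given.

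**Analysis.** Section 7.10.1 uses noncompartmental methods where possible and a sparse-sampling population approach elsewhere. It also plans, without condition, a population PK model to study age, body weight and gender. Section 10.5.1.1 opens with "For subjects in whom the number of samples is sufficient to permit noncompartmental modeling"; where the samples fall is not considered. It then regresses noncompartmental parameters on potential covariates, controlling for demographics such as age and gender, with p = 0.05 as the threshold, and adds: "The multivariable analysis will be considered the primary statistical analysis". Section 10.5.1.2 describes the population model, whose structure is developed on adult data. Details of the PK analysis are left to a separate plan (Protocol Section 10.1; SAP Sections 2.1 and 7.1).

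**The concern.** A noncompartmental Cmax is the highest concentration that happened to be drawn, and Tmax is the time of that draw. If the true peak falls where one group has no samples, that group's Cmax is too low, even when the kinetics are identical in both groups. Here the schedule differs by pubertal group with no overlap, so a schedule effect cannot be separated from a group effect in these parameters.

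The PK profile is a primary endpoint (Section 3.1). The dose was chosen to target a Cmax and AUC like those in adults (Section 1.3), and the study is meant to inform the pediatric regimen (Section 4.2). A downward artefact in the youngest group's peak bears on that comparison even if it is read only descriptively. Using actual collection times corrects clock error but cannot supply a concentration that was never drawn.

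**Working it through.** **1. Does the gap survive the windows?** The 30-minute sample may be 5 minutes late (35 min) and the 2-hour sample 10 minutes early (110 min). The gap is at least 110 - 35 = 75 minutes and always contains 45 minutes.

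**2. Check of the adult inputs.** The 0.75 h is an observed value, so there is no formula to reproduce. The other inputs can be checked. Section 1.2.1 states "Plasma clearance after SC administration of icatibant was 245" mL/min (14.7 L/h), Vss 29.0 L, half-life 1.4 h, and an AUC that "after a single 30 mg dose was 2165" ng·h/mL.
- Half-life: ln 2 × 29.0 / 14.7 = 1.37 h (stated 1.4).
- AUC: 30 mg / 14.7 L/h = 2041. Allowing for averaging 1/CL with clearance CV 58/245 = 0.237, 2041 × (1 + 0.237²) = 2155 (stated 2165).

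The inputs agree with one another.

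**3. Fixed curve, first-order absorption, true Tmax 0.75 h, exact nominal times.** Take C(t) proportional to e^(-kt) - e^(-ka·t), with k = 14.7/29.0 = 0.507/h. Solving ln(ka/k)/(ka - k) = 0.75 gives ka = 2.77/h.
- At 0.75 h: 0.684 - 0.125 = 0.559 (the peak).
- At 0.5 h: 0.776 - 0.250 = 0.526, a ratio of 0.94.
- At 2 h: 0.363 - 0.004 = 0.359, a ratio of 0.64.

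The prepubertal schedule records Tmax 0.5 h and 94% of Cmax; the pubertal schedule records 0.75 h and 100%.

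This curve gives an adult Cmax of 707, not 974, so two other shapes were tried:
- First-order curves forced to AUC 2165, Cmax 974 and Tmax 0.75 h: 909/974 = 93%.
- Zero-order input lasting 0.75 h, as a sharp-peak bound: 633/895 = 71%.

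**4. Variation between subjects.** Simulation of 100,000 subjects per schedule with first-order absorption and the stated windows. Not in the documents, and assumed: CV of ka 30-90%, true median Tmax 0.5, 0.75 or 1.0 h, assay error 0 or 10%.

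| True median Tmax | Assay error | Cmax ratio, prepubertal / pubertal schedule |
|---|---|---|
| 0.5 h | none | 0.97-0.99 |
| 0.75 h | none | 0.93-0.95 (0.92-0.94 of true Cmax v 0.99) |
| 0.75 h | 10% | about 0.90-0.92 |
| 1.0 h | none | 0.88-0.94 |

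Assay error widens the gap partly because the maximum of seven noisy values is pulled up more than the maximum of five.

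Tmax does not move in one direction:
- True Tmax 0.75 h: the prepubertal median is 0.51-0.52 h against a true 0.74 h, but 5-24% of children are recorded near 2 h. Mean Tmax is low with little spread in ka (0.57-0.62 v 0.76 h) and about right with large spread (0.84 v 0.82 h).
- True Tmax 1.0 h: 35-44% are recorded near 2 h, and the mean is too high (1.03-1.18 v 1.01-1.09 h).

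**5. AUC0-6, curve of step 3, linear trapezoid.** -1.5% on the prepubertal schedule and +2.3% on the pubertal one. The gap is about 4 percentage points, more than half of it pubertal overestimation.

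**6. Would the Cmax artefact be declared significant?** Adult CV = 280/974 = 0.287, so the log-scale SD is √ln(1 + 0.287²) = 0.282. With 10 v 20 subjects the standard error is 0.282 × √(1/10 + 1/20) = 0.109. A ratio of 0.94 is |ln 0.94| = 0.062, or 0.57 standard errors. At two-sided 0.05 (sidedness is not stated), the chance that the artefact alone reaches p < 0.05 is 8% at a ratio of 0.94, 16% at 0.90 and 22% at 0.88.

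**The case against.** The strongest reply is that the protocol assigns the age question to the population PK model. Section 7.10.1 plans that model unconditionally for age, weight and gender, and Section 10.5.1.2 expects it to show age-dependent changes in disposition. That stands as partial mitigation, so a reader should not infer that the population model is only a fallback for failed noncompartmental profiles. It does not remove the problem. Noncompartmental methods are still the default where possible, their regression is still labelled primary, and nothing routes prepubertal Cmax or Tmax to the model. With no data from 0.5 to 2 h, a modelled prepubertal peak also leans on an adult-based structure.

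Three other points stand in part:
- Age is an adjustment variable in the Section 10.5.1.1 regression, not its stated target, and no prepubertal v pubertal noncompartmental contrast is specified. Schedule is fully aliased with pubertal group, not with age in years. Results that are set out or regressed together will still be compared.
- The 0.75 h is an adult value. If children peak near 0.5 h, the Cmax bias nearly vanishes. The samples that would settle this directly were not scheduled.
- The separate PK plan may already deal with this. It was not available, and the protocol rule as written does not.

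A reader might also infer that prepubertal AUC is clearly understated. Under the linear rule the prepubertal schedule is the closer of the two to the truth; a prepubertal shortfall of about 5% appears only under the linear-up/log-down rule (0.947 v 0.986 of the true value).

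**Conclusion.** The gap is real, spans the only stated time to peak, and affects one pubertal group only. Noncompartmental Cmax in prepubertal subjects will tend to be underestimated. Relative to the pubertal schedule the shortfall is about 5-10% if true Tmax is near 0.75 h with first-order absorption (the upper end includes 10% assay error). Without assay error it is 1-3% near 0.5 h and up to about 12% on average near 1.0 h. Tmax in that group is unreliable.

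Two stronger readings are tempting and not supported. One is that Tmax is simply biased low: the median is, but the mean can be unbiased or high. The other is that the schedule will by itself produce an age effect. It can contribute to one, but against a CV of about 29% with 10 v 20 subjects it would usually not reach significance. A shortfall of about 29% needs a sharp zero-order peak, which the documents do not suggest.

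The sizes rest on adult kinetics and the assumed spread in ka. Confidence is moderate, because no pediatric Tmax is stated and the PK plan is a separate document. The point should be addressed; it does not invalidate the PK endpoint.

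**What to change.** Section 1.2.2 states that initial treatment is complete, so the change is to the analysis only, in Section 10.5.1.1 and the PK plan:

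1. For any noncompartmental comparison between pubertal groups, and for the regression, also compute pubertal/postpubertal Cmax, Tmax and AUC with the 0.75 h and 1 h samples dropped. Report these beside the full-schedule values, so that both groups are also seen on the same grid.
2. Label prepubertal noncompartmental Cmax as the *highest sampled concentration*.
3. Show population-PK Cmax and Tmax alongside, noting that the prepubertal peak then leans on the adult-based structural model. For that reason the model values should accompany the noncompartmental ones, not replace them.

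Cost: one extra noncompartmental run and a few lines of text, with no new samples. The thinned pubertal values are less precise and serve only the group comparison and the regression check.

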7.10.3 Bioanalytical Method

Plasma samples will be assayed for concentrations of icatibant and its metabolites (M1 and M2) using a validated method (see Section 7.21).

7.11 Efficacy Assessments

7.11.1 Symptom Score

7.11.1.1 Investigator Symptom Score

For subjects treated at the hospital/study center, the investigator will use a symptom score to assess the severities of symptoms of acute cutaneous, abdominal, and laryngeal attacks of HAE using the following 5-point scale. Symptom scores will be recorded on Day 1 at pretreatment and at predetermined time points after treatment. Results will be recorded in the CRF.

Investigator-rated Symptom Score

- 0 = none; absence of symptoms
- 1 = mild (no to mild interference with daily activities)
- 2 = moderate (moderate interference with daily activities)
- 3 = severe (severe interference with daily activities)
- 4 = very severe (very severe interference with daily activities)

For attacks classified as cutaneous and/or abdominal, investigator-rated symptom scores will be collected for 8 symptoms: abdominal tenderness, nausea, vomiting, diarrhea, skin pain, erythema, skin irritation, and skin swelling.

For attacks classified as laryngeal, investigator-assessed symptom scores will be collected for 13 symptoms: abdominal tenderness, nausea, vomiting, diarrhea, skin pain, erythema, skin irritation, skin swelling, dysphagia, voice change, breathing difficulties, stridor, and asphyxia.

